1 STUDY SYNOPSIS

Complete Protocol Title	ASHCOM [™] Shoulder System and Its Related Instruments A Multicenter, Prospective, Non-Controlled Post Market
	Clinical Follow-up Study
Protocol Number	CME2017-67E
Short Protocol Title	ASHCOM [™] Shoulder System and Its Related Instruments
Sponsor	Zimmer GmbH, [name]
Manufacturer	Zimmer Switzerland Manufacturing GmbH, [name]
Study Device(s)	Anaverse [™] Glenoid System
Study Objectives/Endpoints	The objectives of this study are to confirm safety, performance and clinical benefits of the ASHCOM Shoulder System and its related instruments by analysis of standard scoring systems, radiographs and adverse event records. The primary endpoint is defined by the survival of the implant at 10 years which is based on removal or intended removal of the prosthesis and will be determined using Kaplan Meier method. The safety of the system will be assessed by monitoring the frequency and incidence of adverse events. The secondary endpoint of this study is defined by the
	performance and clinical benefits of the ASHCOM Shoulder System at 5 years, which is assessed by the Constant and Murley score. Assessments of the overall pain, functional performance, survival, quality of life and radiographic parameters of all enrolled study subjects will be evaluated- ed in addition.
Indications/Target Population	Patients suffering from severe shoulder pain and disability indicated for implantation of the ASHCOM Shoulder System and who meet all inclusion and none of the exclusion criteria.
Inclusion/Exclusion Criteria	 Inclusion Criteria: Patient is capable of understanding the doctor's explanations, following his instructions and is able to participate in the follow-up program. Patient has given written consent to take part in the study by signing the "Patient Consent Form". Patient is 18-80 years of age, inclusive. Patient is skeletally mature. Patient requires a primary, fracture or revision reverse total shoulder replacement for the relief of pain and has significant disability due to gross rotator cuff deficiency.

	 Patient's joint is anatomically and structurally suited to receive the selected implants. Patient has a functional deltoid muscle. Exclusion Criteria: Patient is unwilling or unable to give consent or to comply with the follow-up program. Patients who have any condition which would in the judgement of the Investigator place the patient at undue risk or interfere with the study. Any patient who is institutionalized, or is a known drug abuser, a known alcoholic or anyone who cannot understand what is required of them. Patient is known to be pregnant or breastfeeding.
	 Patient is a vulnerable subject. Patient meets at least one of the contraindications: Signs of infection Significant injury to the upper brachial plexus Non-functional deltoid muscle Insufficient quality and/or quantity of glenoid or humeral bone Any neuromuscular or vascular disease compromising the affected limb that would endanger the success of the intervention
Study Design	A multicenter, prospective, non-controlled post market surveillance study
Clinical Phase	Post-market
Sample Size	97 shoulders.
Length of Study	12 years (2 years enrollment plus 10 years follow-up): follow-up visits at 3 to 6 months, 1, 2, 5, and 10 years. Follow-up surveys at 3 and 7 years post-operatively.
Materials and Methods	Case report forms will be completed either in-office or hospital at Pre-op, Surgery, Discharge, and at the 3-6 months and at 1, 2, 5 and 10 year post-operation intervals. Patient completed follow-up surveys will be conducted at 3 and 7 years after surgery.
Data Collection	Paper/Electronic
Statistical Reporting	Data collected will be summarized and reported to each participating investigator. Statistical analysis will be

	conducted by Zimmer Biomet or its designee. Survivorship will be evaluated using Kaplan-Meier.
Scores/Performance Assessments	Constant-Murley, Oxford Shoulder Score, EuroQol (EQ-5D), Patient Satisfaction, Revisions, Adverse Events, Radiographic Assessment.
Standards	 The PMCF is compliant with the below: ISO 14155: 2020 - Clinical investigation of medical devices for human subjects - Good clinical practice. The Declaration of Helsinki (DoH) – Ethical principles for medical research involving human subjects. European Regulation (EU) 2017/745.
Study Funding	Funding for this clinical study is made available by Zimmer Biomet to support clinical data collection, IRB/EC review fees and other expenses associated with the conduct and execution of this study protocol as outlined in the fully executed Clinical Trial Agreement.

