2 STATISTICAL ANALYSIS PLAN

2.1 Sample Size

This study is designed to have an alpha error no greater than 0.05. Based on an assumed survivorship of 86% at ten years, a sample size of n = 58 at ten years has at least 80% probability to compute a one-sided 95% lower confidence bound on the survivorship of the device with a half-width precision of 0.09. Sample size calculation was computed using SAS 9.4, Proc Power. To account for loss-to-follow-up estimated at 5% per year, 97 patients need to be enrolled in the study to have 58 patients at the end of ten years.

The half-width precision of 0.09 allows us to set a lower bound on survivorship of 9% from the expected survivorship performance of 86% at 10 years. This detectable change of 9% is analogous to non-inferiority margins that approach 10% in regulated studies

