2.2 Statistical Analysis

Continuous data (e.g. age, BMI, Oxford Shoulder Score) will be reported using mean, standard deviation, median, and range. Comparisons between continuous baseline and interim patient visits will be performed using standard statistical tests and will be chosen as appropriate for the scale and distribution of the measures being analyzed. For example, a t-test, Wilcoxon test, or one-way ANOVA (as appropriate) may be performed to assess differences. Comparisons between preoperative and follow-up visit scores will use two-sided comparisons with $\alpha = 0.05$, with no adjustment for multiple comparisons.

Categorical data (e.g. gender) will be reported using frequency and percentage. Comparisons between categorical baseline and interim patient visits will be performed using standard statistical tests and will be chosen as appropriate for the scale and distribution of the measures being analyzed.

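### Does adverse-event incidence need a stated unit, denominator and handling of loss before the safety results can be read?

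*Combined protocol and SAP*

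**What the plan says.** The synopsis (Study Objectives/Endpoints) opens with "The objectives of this study are to confirm safety, performance and clinical benefits" of the system and gives one operational sentence on safety: "The safety of the system will be assessed by monitoring the frequency and incidence of adverse events". The list of assessments in the synopsis includes "Patient Satisfaction, Revisions, Adverse Events, Radiographic Assessment", without further definition.

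SAP 2.2 does not name adverse events. Its nearest rule is general: "Categorical data (e.g. gender) will be reported using frequency and percentage". It gives no denominator. Kaplan-Meier is named only for implant survival, where the event is removal or intended removal.

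Loss appears only in SAP 2.1, to size enrolment: "To account for loss-to-follow-up estimated at 5% per year", with the result that "97 patients need to be enrolled in the study to have 58 patients at the end of ten years". The Sample Size row of the synopsis gives the same 97 as shoulders. Neither place says whether one patient may contribute two shoulders.

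**The concern.** Confirming safety is a stated objective, and there is no control arm, so the reported adverse-event figure has to be interpretable on its own. The synopsis names frequency and incidence separately, which suggests that incidence is meant to be more than a raw count.

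The plan itself expects about 40% of those enrolled to be gone by year ten (97 down to 58). With that much loss, a share of those enrolled, a share of those still followed, a person-time rate and a ten-year risk are four different quantities. A reader given a single unlabelled percentage could not tell which it was. If a share of the enrolled were taken for a ten-year risk, it could be too low; a share of the 58 remaining could be too high. Having two units for the 97 adds a second doubt about the denominator. Settling the definition only when the tables are made would also leave room to choose it after seeing the data.

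**Working it through.** **The plan's own figure.** From SAP 2.1: 58 at ten years, 5% loss per year. 58 / 0.95^10 = 96.87, rounded up to 97; in reverse, 97 × 0.95^10 = 58.1. The arithmetic behind 97 reproduces.

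**Inputs for the illustration.** Taken from the documents: 97 enrolled, 5% yearly loss, ten years. Assumed, because the documents give no adverse-event rate: 10 of 97 have a first event. The timing of events and the share of loss that is death are also assumed, and are varied below.

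**Simple summaries of the same 10 patients.**
- Of those enrolled: 10/97 = 10.3%.
- Of those remaining: 10/58 = 17.2%.
- Person-time under a constant hazard: the loss hazard is c = −ln(0.95) = 0.05129. Solving 97 × h/(h+c) × (1 − exp(−10(h+c))) = 10 gives h = 0.01404. Time at risk to first event is 10/0.01404 = 712 patient-years, or 1.40 per 100.

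**Ten-year cumulative incidence.** Let the event hazard h act between years a and b, and let the death hazard be d = (death share) × c. Then

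CI = exp(−a·d) × h/(h+d) × (1 − exp(−(h+d)(b−a))).

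Each h is set so that 10 first events are expected among 97.

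| Event timing | h | No loss is death | Half | All |
|---|---|---|---|---|
| Constant over ten years | 0.01404 | 13.1% | 11.6% | 10.3% |
| All in year 1 | 0.1117 | 10.6% | 10.4% | 10.3% |
| All in year 10 | 0.1835 | 16.8% | 13.1% | 10.3% |

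The relative shortfall of the 10.3% share is 1 − 10.31%/CI:

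| Event timing | No loss is death | Half | All |
|---|---|---|---|
| Constant over ten years | 21% | 11% | 0% |
| All in year 1 | 2.5% | 1.2% | 0% |
| All in year 10 | 39% | 22% | 0% |

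The documents do not select a row or a column.

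**Against sampling error.** The largest constant-hazard gap is 13.1 − 10.3 = 2.8 points. The binomial standard error of the crude share is √(0.103 × 0.897 / 97) = 0.031, or 3.1 points. In simulated studies of 97, the loss-adjusted estimate has a standard error of 4.0 points when no loss is death and 3.0 when all of it is. The constant-hazard gap is below one standard error throughout.

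**The unit of 97.** If 97 counts shoulders and an assumed 5% or 10% of patients contribute both, there are 97/1.05 = 92.4 or 97/1.10 = 88.2 patients. Ten affected patients are then 10.8% or 11.3%, against 10.3%. If nobody contributes both shoulders, nothing changes.

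**What would depend on the figure.** Neither the synopsis nor the SAP sets an adverse-event threshold, a safety hypothesis or a stopping criterion based on adverse events. The sample size rests on implant survivorship alone. No result in the tables above feeds a planned decision.

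**The case for a change.** The strongest case for a change is that the gap is real and cheap to close. No text supplies a denominator: Kaplan-Meier is confined to survival, the 5% loss is used only to size the study, and SAP 2.2 is silent on what its percentages are percentages of. Two careful analysts could report different rates for the same 10 patients: 1.40 per 100 if time stops at the first event (712 patient-years), or 10/759 = 1.3 per 100 if all expected follow-up is counted (97 × (1 − 0.95^10)/0.05129 = 759). A few sentences would remove the doubt.

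The factual part of this stands: the definition is absent from the text available, and the two units for 97 are inconsistent. The inference that the plan is therefore faulty does not follow. Having or not having an adverse event is categorical data, and gender in SAP 2.2 is an example rather than a closed list, so the natural output is a number and a percentage. That describes what was observed correctly whether or not some patients were lost. Dividing by 58 is not proposed anywhere; in SAP 2.1 that number is only the target for precision at ten years. Presenting the crude share as a ten-year risk is not proposed either. Choosing a cumulative incidence or a person-time rate for descriptive safety data is good practice, but it does not correct an error here. Either would also be limited by the contact schedule: after year 2 the planned contacts fall at 3, 5, 7 and 10 years, those at 3 and 7 by patient survey, so some event dates may be approximate.

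On the unit, the inclusion criteria speak of the patient's joint in the singular and SAP 2.1 speaks of patients throughout. That fits one shoulder per patient without excluding two.

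**Conclusion.** No change follows. The missing definition is a gap that analysts ordinarily fill when they lay out the tables, by showing counts with a labelled denominator and, given the planned loss, numbers at risk or patient-years beside them. The mismatch between shoulders and patients is a clerical inconsistency unless bilateral enrolment occurs, which no text states.

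The shortfall of 0% to 39% rests on 10 assumed events, on assumed timing and death share, and on reading a crude percentage as a ten-year risk. Its upper end needs every event in year 10 and no deaths among the losses. It is not evidence of bias in this study. No stated rule gives a wrong result, and the 97, the 58 and the primary Kaplan-Meier analysis are untouched. The event that matters most for the device, removal or intended removal, already has a method that handles censoring. The conclusion is limited to the synopsis and SAP; a fuller investigation plan might define incidence, but the conclusion does not depend on that.

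### The 5- and 10-year contacts are clinic-based, with no remote contact described for patients who miss them, although the plan expects 40% cumulative loss; an implant-status survey for non-attenders could recover some primary outcomes

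*Combined protocol and SAP*

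**What the plan says.** The Synopsis (Study Objectives/Endpoints) defines the primary endpoint as "survival of the implant at 10 years which is based on removal or intended removal of the prosthesis", which "will be determined using Kaplan Meier method".

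Under Materials and Methods it says "Case report forms will be completed either in-office or hospital" at the perioperative time points, at 3 to 6 months, and at the "1, 2, 5 and 10 year post-operation intervals". The next sentence adds: "Patient completed follow-up surveys will be conducted at 3 and 7 years after surgery". No survey is scheduled at 5 or 10 years, and no telephone, postal or records-based contact is described for a patient who misses those visits.

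The Scores/Performance Assessments row also lists "Patient Satisfaction, Revisions, Adverse Events, Radiographic Assessment", without saying when or how revisions and adverse events are ascertained.

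Section 2.1 says: "To account for loss-to-follow-up estimated at 5% per year, 97 patients need to be enrolled", leaving 58 at ten years. Section 2.2 describes no analysis of how the result would change if loss were related to implant failure.

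**The concern.** Kaplan-Meier censors a lost patient at last contact and treats later removal risk as equal to that of patients still followed. A patient whose shoulder fails may be treated elsewhere and not return. If so, the estimate overstates survivorship. Enrolling more patients restores numbers but does not correct this.

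The endpoint needs little information: whether the prosthesis was removed or is planned for removal, and when. The study already runs a patient-completed survey, but not at the two late visits and not as a fallback for non-attenders. Outcomes that might be obtained cheaply may therefore be lost, and the plan offers no view of how much the result depends on the censoring assumption.

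**Working it through.** **Inputs from the plan.** 97 enrolled, 58 at ten years, 5% loss per year, 86% survivorship, one-sided 95% lower bound, half-width 0.09 (section 2.1). The implied floor is 86 − 9 = 77%.

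**Inputs assumed.** Constant removal and loss hazards; removal hazard after loss is HR times that of retained patients, with HR 1.5, 2 or 3. The documents give no value for HR or for survey response.

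**1. The plan's figures.** 0.95^10 = 0.599, so cumulative loss is 40.1%. 58/0.599 rounds up to 97, and 97 × 0.599 = 58.1. The enrolment figure reproduces. The 58 also reproduces: at 86%, the probability that half the width of a Clopper-Pearson interval (5% per tail) is at most 0.09 is 0.819 at n = 58 and 0.729 at n = 57.

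**2. Removals and losses.** λ = −ln(0.86)/10 = 0.01508 and c = −ln(0.95) = 0.05129 per year. The chance of either event by year 10 is 1 − 0.86 × 0.599 = 0.485.
- Observed removals: 97 × λ/(λ+c) × 0.485 = 10.7
- Lost before removal: 97 × c/(λ+c) × 0.485 = 36.4

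**3. Bias.** True survivorship when Kaplan-Meier reads 86%:

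S(HR) = e^(−10(λ+c)) + ∫₀¹⁰ c·e^(−(λ+c)t)·e^(−HR·λ(10−t)) dt

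At HR = 2 this is 0.515 + 0.318 = 0.833.

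**4. Lower bound.** The Greenwood SE is 0.86 × √{[λ/(97(λ+c))] × (e^(10(λ+c)) − 1)} = 0.86 × √(0.002343 × 0.942) = 0.0404. On the log-log scale the SE is 0.0404/(0.86 × 0.1508) = 0.3115, and e^(1.645 × 0.3115) = 1.669, so the bound is S^1.669 (log-log SE held fixed). The plain bound is S − 1.645 × 0.0404 = S − 0.0665.

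| HR (assumed) | True survivorship | Bias (points) | Log-log bound | Plain bound |
|---|---|---|---|---|
| 1 | 86.0% | 0 | 77.7% | 79.4% |
| 1.5 | 84.6% | 1.4 | 75.7% | 78.0% |
| 2 | 83.3% | 2.7 | 73.7% | 76.7% |
| 3 | 80.9% | 5.1 | 70.2% | 74.3% |

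**5. Tipping ratio at 77%.**
- Log-log bound: S^1.669 = 0.77 needs S = 0.855, which is HR about 1.2.
- Plain bound: S = 0.77 + 0.0665 = 0.8365, which is HR about 1.9.
- Point estimate: S = 0.77, which is HR about 4.9.

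The plan does not name the form of its Kaplan-Meier bound.

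**6. When the bias arises (HR = 2).** The integral of c·e^(−(λ+c)t)·[e^(−λ(10−t)) − e^(−2λ(10−t))] over each interval gives:

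| Time of loss | Patients lost before removal | Bias (points) | Share |
|---|---|---|---|
| Years 0–5 | 21.2 | 2.10 | 78% |
| Years 5–7 | 6.7 | 0.38 | 14% |
| Years 7–10 | 8.5 | 0.20 | 7% |
| Total | 36.4 | 2.68 | 100% (rounded) |

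**7. Precision.** Suppose a share q of lost patients is recovered evenly over loss times. Replacing e^(−ct) by q + (1−q)e^(−ct) in Greenwood's formula gives an SE of 0.0404, 0.0397, 0.0388 and 0.0375 for q = 0, 10%, 25% and 50%.

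**The case against.** A reader might infer that implant status is recorded only at the clinic visit. The documents do not support that. The outcome is time to event, removals can enter at any earlier visit, and revisions and adverse events are listed as separate data with no stated mode. The Materials and Methods sentence says where forms are completed; it does not forbid a site from completing one after a telephone call. The available text is a synopsis and a short SAP. What remains is that no such contact is described, and that a record of removals does not establish that an absent patient's implant is in place.

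A reader might also infer that the survey would recover the missing 40% and remove a proportionate share of bias. At HR 2, even recovery of 25% or 50% would leave roughly 2.68 × 0.75 = 2.0 or 2.68 × 0.50 = 1.3 points. Nothing in the documents supports even recovery. Someone lost before year 7 has, in effect, already not answered the year-7 survey. If only patients lost after year 7 could be reached (97 × (0.95^7 − 0.95^10) = 9.7), known status would rise from 58 to at most about 68, and about 7% of the modelled bias would go. Deaths, whose share of the 5% is not given, are not recoverable, and the model wrongly gives them continuing removal risk.

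Nor do the documents show that loss is related to failure: every HR above 1 is an assumption, and at 1.5 the bias is about one third of one SE (1.4 against 4.0 points). The expected loss is already allowed for in the enrolment figure, so this is not a sample-size error.

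Finally, the 4.9 ratio for the point estimate might be read as reassurance. The plan's 9-point margin applies to the lower bound, which reaches 77% at a much smaller ratio.

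**Conclusion.** The point holds as a low-cost improvement. The scheduled 5- and 10-year contacts are clinic-based, no remote contact is described for those who miss them, and the plan's own figures imply 40% cumulative loss. Under constant hazards the primary estimate rests on about 11 removals, with about 36 patients censored by loss. Bias would be 1.4 to 5.1 points for assumed hazard ratios of 1.5 to 3.

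The lower bound has little room. With a log-log bound it stands at 77.7% before any bias and reaches 77% at a ratio of about 1.2; with a plain bound the ratio is about 1.9. The 77% is the floor implied by the precision statement, not a stated pass mark.

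A remote status contact could recover some outcomes and reduce possible bias. How much depends on response and on timing: the year-5 contact and re-contact of earlier losses matter most. The precision gain is modest (SE 0.0404 to 0.0388 at 25% recovery).

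**What to change.** 1. State that any patient who misses the 5- or 10-year visit is sent the existing patient survey with added questions on implant status: removed or planned for removal, and the date. State that patients lost earlier are also tried again at these time points.
2. State that all responses, failed or not, enter the primary Kaplan-Meier analysis. Counting only recovered failures would bias the estimate the other way.
3. For those still lost, prespecify a sensitivity table with post-loss removal hazard at 1.5, 2 and 3 times that of retained patients, giving both the estimate and its one-sided 95% lower bound. Name the form of the bound, and report the ratio at which the bound reaches 77% rather than the ratio for the point estimate.

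The cost is a short amendment, a few survey items (the survey's present content is not given), mailing or telephone effort for non-attenders, and one table. The downside is that patient-reported status, especially intended removal, is less certain than a clinic record, so the source of each status should be recorded.

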2 STATISTICAL ANALYSIS PLAN

2.1 Sample Size

This study is designed to have an alpha error no greater than 0.05. Based on an assumed survivorship of 86% at ten years, a sample size of n = 58 at ten years has at least 80% probability to compute a one-sided 95% lower confidence bound on the survivorship of the device with a half-width precision of 0.09. Sample size calculation was computed using SAS 9.4, Proc Power. To account for loss-to-follow-up estimated at 5% per year, 97 patients need to be enrolled in the study to have 58 patients at the end of ten years.

The half-width precision of 0.09 allows us to set a lower bound on survivorship of 9% from the expected survivorship performance of 86% at 10 years. This detectable change of 9% is analogous to non-inferiority margins that approach 10% in regulated studies

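### Does leaving death out of the attrition allowance and the Kaplan-Meier plan undermine the ten-year implant survivorship estimate?

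*Combined protocol and SAP*

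**What the plan says.** The SAP, section 2.1, sets the precision target for the primary endpoint. The starting point is stated as "Based on an assumed survivorship of 86% at ten years". The plan then claims that "a sample size of n = 58 at ten years has at least 80% probability" of reaching its target. That target is a "one-sided 95% lower confidence bound on the survivorship of the device", and its precision is given as a half-width of 0.09. Enrolment is then raised from 58 to 97 in one step: "To account for loss-to-follow-up estimated at 5% per year, 97 patients need to be enrolled in the study to have 58 patients". The 58 refers to year ten.

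The synopsis admits older patients ("Patient is 18-80 years of age, inclusive") and follows each for ten years. The primary event is removal of the prosthesis, or an intention to remove it. On method the synopsis says "Survivorship will be evaluated using Kaplan-Meier". Neither part says whether the 5% covers deaths, how a death enters the survivorship analysis, or which type of Kaplan-Meier confidence limit will be used.

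**The concern.** Some patients in this age range will die with the implant in place during ten years of follow-up. If the 5% means only patients who drop out of contact, the plan keeps 58 at ten years only if nobody dies. The 58 and its 80% probability are the only planning figures for the primary endpoint, so both would seem to be at risk.

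There is also a question of what is estimated. Death is not an event, so a standard Kaplan-Meier analysis censors it. The result is a net survivorship, as if nobody died, and one minus that figure overstates the share of patients who actually have an implant removed.

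**Working it through.** **Inputs from the documents.** Ten-year survivorship 0.86; one-sided 95% bound; half-width 0.09; 80% probability; 58 at ten years; 5% loss per year; 97 enrolled (SAP 2.1). Kaplan-Meier analysis (synopsis).

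**Assumptions.** Added mortality m of 1% to 4% per year, independent of loss and of removal; constant hazards.

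**1. The plan's own figures.** 58 / 0.95^10 = 58 / 0.5987 = 96.87, rounded up to 97. In reverse, 97 × 0.95^10 = 58.08. The 58 is reproduced by half the width of an exact (Clopper-Pearson) interval with 5% in each tail at p = 0.86: P(half-width ≤ 0.09) is 72.9% at n = 57 and 81.9% at n = 58.

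**2. Patients left if deaths are additional.** 97 × [0.95 × (1 − m)]^10 gives 52.5, 47.5, 42.8 and 38.6 for m = 1%, 2%, 3% and 4%. Applying the binomial calculation of step 1 to those numbers, rounded down, gives 55%, 51%, 28% and 20%. That would be a real loss, but it describes an analysis of ten-year completers only, which is not the planned analysis. It is also jumpy: at m = 1%, n = 52 gives 55% and n = 53 gives 68%.

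**3. Precision of the planned analysis.** Kaplan-Meier uses all 97 patients until they leave. With h = −ln(0.86)/10 = 0.01508 and exit hazard c = −ln(0.95) − ln(1 − m), the approximate Greenwood half-width is

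1.645 × 0.86 × √{ h / [97(h + c)] × (e^{10(h + c)} − 1) }.

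With no deaths, c = 0.05129 and this is 1.645 × 0.86 × √0.002207 = 0.066. The probabilities below come from simulating 97 patients with exponential removals (20,000 runs; repeat runs differ by up to about half a point).

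| Added mortality per year | Left at ten years | Greenwood half-width | P(half-width ≤ 0.09), plain limits | P(half-width ≤ 0.09), log-log limits |
|---|---|---|---|---|
| 0% | 58.1 | 0.066 | 99.9% | 99.8% |
| 1% | 52.5 | 0.068 | 99.4% | 99.3% |
| 2% | 47.5 | 0.070 | 98.0% | 97.5% |
| 3% | 42.8 | 0.072 | 95.8% | 94.5% |
| 4% | 38.6 | 0.075 | 91.7% | 89.4% |

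Every entry in the last two columns is above 80%.

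**4. Net survivorship against actual removal risk.** With death hazard μ = −ln(1 − m), the ten-year cumulative incidence of removal is h/(h + μ) × (1 − e^{−10(h + μ)}). For m = 1% to 4% this is 13.3%, 12.7%, 12.1% and 11.6%, against 14.0% for one minus Kaplan-Meier. The gaps are 0.7, 1.3, 1.9 and 2.4 points, and in each case Kaplan-Meier shows the higher removal risk.

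**The case for a change.** The best case for a change is that the text does not say the 5% includes deaths, that one sentence would settle it, and that the precision depends on a confidence limit the plan does not name. The last point has some substance. SAP 2.1 also describes the 0.09 as how far the lower bound lies below 86%. If precision is measured as the distance from the estimate to a log-log lower limit, the probability of staying within 0.09 is 86% with no deaths and falls to about 74%, 60%, 47% and 37% at 1% to 4% added mortality.

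That combination is not the plan's. SAP 2.1 states a half-width and names no log-log limit. The distance measure also fails to reproduce the plan's own number: for the exact interval at n = 58, the distance to the lower limit is within 0.09 with only 16% probability, and 80% is first reached at n = 74. With log-transformed limits, even the distance measure stays within 0.09 with about 97% probability or more. One unstated combination therefore falls short, which does not establish that the study does.

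It is also fair to say that deaths and losses should be told apart in the data, and that the cumulative incidence of removal is informative for patients. The synopsis already plans adverse-event records, where deaths would be expected to appear. The cumulative incidence answers a different question from implant survival, so it is an optional supplement.

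What stands is that the wording could be clearer, and that 58 would be missed if deaths come on top of the 5%.

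**Conclusion.** No change is needed. The plan has one attrition term and does not exclude deaths from it; read as attrition from all causes, it leaves 97 and 58 as they are. If deaths are extra, the count at ten years falls to about 52 to 39 for an assumed 1% to 4% yearly mortality. The half-width target is still met with about 89% to 99% probability, because Kaplan-Meier also uses follow-up from patients who leave early.

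An analyst following the plan would censor deaths with the implant in place. That fits an endpoint about the device, and the result should be read as net implant survivorship. Its departure from the removal risk patients actually face, 0.7 to 2.4 points, is against the device.

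These figures rest on assumed death rates, constant hazards, and deaths independent of both loss and removal. They apply to the half-width as SAP 2.1 states it, with plain or log-log limits. The silence on death is a gap that ordinary practice fills sensibly.
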